2.1.9. Effectiveness Analysis

There is a formal test of hypotheses for the primary endpoint. Other p-values that are generated for other endpoints will be regarded as descriptive statistics. Imagio (IUS+OA) represents the reader input after viewing the Imagio (IUS+OA) images and SenoGram results. IUS represents the reader input prior to any IUS feature scoring, but after reader training on Imagio (IUS+OA).

The following will be used to assess the pivotal study.

Table 1: Effectiveness Analysis for Study Endpoints

Endpoints by Cohort	Analysis/Software
Primary	
Gain in specificity Imagio (IUS+OA) vs. IUS at fixed 98% sensitivity interpolated from the ROC AUC curves using methods of Obuchowski-Rockette (OR). Effect estimates (two-sided 95% CIs) will be derived using OR-DBM MRMC methods. The interim analysis to re-assess pivotal study sample size will be determined using OR-DBM MRMC sample size program.	OR-DBM MRMC Sample Size: OR-DBM-MRMC Power program, nQuery v7, SAS (PROC POWER), and/or PASS v15.0.5.

Secondary	

Partial AUC: Difference (Imagio (IUS+OA) vs. IUS) in partial Receiver Operator Characteristic (ROC) Area Under the Curve (AUC) for 95-100% sensitivities using the OR methods.
	
OR-DBM

Specificity and Sensitivity: Specificity is defined using the percent with a negative result (POM <2%) among all benign+TPB masses (to include all high-risk masses). Sensitivity is defined using the percent with a positive result (POM >2%) among all malignant masses.
 
Observed and model-adjusted specificity and sensitivity will be reported for Imagio (IUS+OA) vs. IUS using a 2% Probability of Malignancy (POM) cutoff.
 
These analyses will be repeated for POM cutoffs of 1%, 3%, 4%, 5%, 6%, and 7%.
 
High risk masses will be included in the calculations for specificity.
	
SAS PROC GEE and MIXED treating masses as independent observations and readers as correlated and then readers as independent and masses as correlated.
 
Two-sided 95% confidence intervals (CIs) for sensitivity and specificity will be computed for IUS, for Imagio (IUS+OA), and for the pairwise difference.
 
Confidence intervals will be constructed treating masses as independent observations with readers as correlated and then readers as independent with masses correlated.


Negative Likelihood Ratios (NLR) and Positive Likelihood Ratio (PLR) for IUS and Imagio (IUS+OA), NLR defined as $((1 - \text{observed sensitivity}) / \text{observed specificity})$, and relative NLR and PLR for paired designs.
	
SAS: Univariate 95% CI for PLR and NLR with variances fit using the logarithmic transformation and the delta method, reference PIONEER Table 14.2.3.2.
 
MATLAB script: XXXXXXXXXX

SenoGram performance using the following metrics from the study endpoints:
 
 a) Sensitivity and specificity for SenoGram classification based on predicted probability and the SenoGram threshold, with subgroup analysis for masses with and without mammogram BI-RADS data. b) Specificity at fixed sensitivity (98%) for SenoGram classification as in (a). c) Partial AUC (over 95% to 100% sensitivity, inclusive) for SenoGram classification as in (a). 	
For each metric, a summary table for each reader (where appropriate) and for all readers to contain the following:
 
 • Measured value using READER-02 feature data. • Estimated value from SenoGram cross-validation with PIONEER feature data. • Estimated value from SenoGram predictions for masses with PIONEER data.
Exploratory	

OA Feature Score Distributions:
 
 • Benign vs. malignant masses • Benign masses only – mammogram vs no mammogram 
POM Score Distributions:
 
 • Benign vs. malignant masses • Benign masses only – mammogram vs no mammogram 
Inter-reader variability assessments (POM and feature scoring):
 
 • Mammogram • IUS • OA. 	
Summary Statistics by reader. Average over readers and then summarize means for overall. Use a Wilcoxon Rank Sum test.
 
Reference PIONEER T14.2.10.1 [t_14_02_1x_feat-10-_01]
 
Reference PIONEER Table 14.2.9.1 [t_14_02_09_pom-01]
 
Statistics will be calculated to assess inter-reader variabilities.

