11. GRAPHICAL INTERFACE FOR BI-RADS CATEGORY AND POM RATING

For the purpose of this study, the readers will use a graphical interface to assist them in their assessment of applying their POM to the BI-RADS category for IUS and Imagio (IUS+OA).

The POM scale is linear for all BI-RADS categories; however, the scale for BI-RADS 3 is expanded ten-fold compared to other categories. This design allows for a finer gradation of the malignancy rating for BI-RADS 3 lesions, which in turn provides more data points for the ROC curve and enables a better estimation of the partial AUC. One advantage of a

graphical metaphor is that it provides an aid to the Reader in assigning first a POM score and then a BI-RADS category.

Figure 3: Graphical input of BI-RADS category and POM rating

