2.1.10. Hypotheses to be Tested

The test of the primary hypothesis is powered to detect a 10% absolute specificity advantage (superiority) as the alternative hypothesis with no specificity advantage as the null hypothesis. The primary endpoint will be evaluated in the following testable hypotheses:

$$H_0: S_{\text{Imagio}} = S_{\text{IUS}}$$

$$H_1: S_{\text{Imagio}} \neq S_{\text{IUS}} \text{ representing a 10\% absolute increase}$$

where S_{Imagio} and S_{IUS} represent specificity, values associated with Imagio (IUS + OA) and IUS.

The following hypothesis tests will be applied using the observed estimates for the following secondary endpoints:

- NLR:
 - $H_0: \text{NLR}_{\text{IUS}} = \text{NLR}_{\text{Imagio}}$ vs
 - $H_A: \text{NLR}_{\text{IUS}} \neq \text{NLR}_{\text{Imagio}}$ representing a reduction
- PLR:
 - $H_0: \text{PLR}_{\text{IUS}} = \text{PLR}_{\text{Imagio}}$ vs
 - $H_A: \text{PLR}_{\text{IUS}} \neq \text{PLR}_{\text{Imagio}}$ representing an increase
- Partial ROC AUC:
 - $H_0: \text{pAUC}_{\text{IUS}} = \text{pAUC}_{\text{Imagio}}$ vs
 - $H_A: \text{pAUC}_{\text{IUS}} \neq \text{pAUC}_{\text{Imagio}}$ representing an increase

Hierarchical testing will be applied to seek labeling claims if warranted by the pre-defined testing procedure (see Section 2.1.11.4).

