2.1.11. Data Analysis Methodology

Data Analyses

As for the PIONEER Pivotal Study, analyses will be based on independent readers for POM, BI-RADS and feature scores (IUS, Imagio (IUS+OA)) individually and overall. There is a formal hypothesis test for the primary endpoint and the three secondary endpoints. Hierarchical testing will be in place to control the Type I error. Truth (determination of malignant biopsy, benign biopsy, HR or TPB) will be taken from the PIONEER Pivotal Study. All CB masses (n=29) will be excluded from all analyses; these masses will be replaced in order to preserve final analysis power.

The specificity advantage of Imagio (IUS+OA) vs. IUS will be compared at fixed 98% sensitivity. The software package OR-DBM MRMC [Version 2.5 or later] will be used for this analysis of OA gain as interpolated from the ROC curves.

Specificity and sensitivity will be calculated by reader and overall for IUS, Imagio (IUS+OA), and the pairwise difference [PROC GENMOD, see Table 1]. Specificity and sensitivity will be calculated using the 2% POM cutoff for IUS and for IUS+OA; and then for 1%, 3%, 4%, 5%, 6%, and 7% cutoffs to assess robustness. In clinical practice, the POM Scores (0-100) are standardized such that a BI-RADS 3 (probably benign) shows a likelihood of cancer to be > 0% up to 2% inclusive.

Specificity and sensitivity are calculated using this fixed 2% cutoff. Please be assured that the OR-DBM MRMC 2.51 (Hillis) software does not pick or use a fixed cutoff. [REDACTED]

[REDACTED] The gain in specificity can be computed at a wide range of sensitivities. The 98% sensitivity corresponds to a 2% false negative (FN) rate, but this unrelated to the use of a fixed 2% POM cutoff for clinical decision making.

NLR and PLR will be analyzed using the logarithmic transformation and the delta method. Calculations will be performed using MATLAB script: [REDACTED] [REDACTED]

Last, pAUC for fixed 95% to 100% sensitivity will also be analyzed using OR-BDM MRMC.

The sample size for the READER-02 pivotal study was calculated using method implemented in the MRMC Sample Size Program 1.0 for Diagnostic Studies, by Hillis, Obuchowski, and Birnbaum. These sample size results may be confirmed by other packages such as nQuery, PASS, and SAS [PROC POWER].

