2.1.11.4. Multiple Comparisons / Multiplicity

To extend labeling claims beyond the primary endpoint, a hierarchical testing strategy will be used to control Type 1 error associated with testing the primary endpoint and three secondary endpoints in the following pre-defined order until statistical significance is no longer reached in support of extended labeling:

- Increase in specificity for fixed 98% sensitivity.
- Decrease in NLR
- Increase in PLR
- Increase in pAUC over 95% to 100% sensitivity

No other endpoints are to be included as labeling claims.

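### SAP Table 1 scores a POM of exactly 2% as an error for both benign and malignant masses, so sensitivity, specificity, NLR and PLR do not rest on one cut-point

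*Combined protocol and SAP*

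**What the plan says.** Table 1 in SAP 2.1.9 gives two definitions. For benign masses: "Specificity is defined using the percent with a negative result (POM <2%) among all benign+TPB masses". For malignant masses: "Sensitivity is defined using the percent with a positive result (POM >2%) among all malignant masses". The table describes this as a 2% POM cutoff and repeats the analysis at 1%, 3%, 4%, 5%, 6% and 7% without giving an inequality for those values.

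SAP 2.1.11 says that in clinical practice "BI-RADS 3 (probably benign) shows a likelihood of cancer to be > 0% up to 2% inclusive". Its next paragraph says "Specificity and sensitivity are calculated using this fixed 2% cutoff", a sentence that also stands in Protocol 10.9.

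The following row of Table 1 covers NLR, PLR and "relative NLR and PLR for paired designs", with NLR built from observed sensitivity and observed specificity. SAP 2.1.10 then says: "The following hypothesis tests will be applied using the observed estimates for the following secondary endpoints". Under SAP 2.1.11.4, NLR and PLR are steps two and three of a sequence covering the primary endpoint and "three secondary endpoints in the following pre-defined order until statistical significance is no longer reached". On data capture, Protocol 11 says that "the scale for BI-RADS 3 is expanded ten-fold compared to other categories".

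**The concern.** Both inequalities are strict and both denominators include every mass of the given truth status. A read of exactly 2% is not dropped. It fails the specificity definition if the mass is benign and the sensitivity definition if the mass is malignant. In effect specificity treats 2% as positive and sensitivity treats it as negative. A binary test cannot do both, because the coding would then depend on the truth.

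This matters beyond the descriptive sensitivity and specificity. NLR and PLR take that pair as inputs and support labeling claims if the hierarchy reaches them. SAP 2.1.11 says the secondary endpoints have formal tests. SAP 2.1.9 calls non-primary p-values descriptive, but that is a separate conflict.

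Ties at 2% are plausible, since 2% is the upper edge of BI-RADS 3 and readers set POM and BI-RADS on a linked graphical scale. Nor can equal tie shares in the two reads be assumed: the Read 2 POM is given after viewing the SenoGram and the Read 1 POM is not. If the wording stays, the programmer must either code an incoherent rule or choose a tie rule without guidance from the plan.

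**Working it through.** **Are the symbols reliable?** The SAP Summary of Changes (V2.0 entry) shows the same two strict signs, and a greater-than-or-equal sign survives elsewhere in SAP 2.1.8. A symbol lost in text extraction is therefore unlikely.

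**The plan's own figure.** The only computed design figure is 854 image sets at power 0.801. It was reproduced from the listed variance components (power 0.800 at 854 and 0.795 at 840, against the SAP's 79%). No POM cutoff enters that calculation. The primary endpoint and pAUC come from the ROC curve and do not use one either.

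**Definitions**
- se = P(POM > 2% given malignant); sp = P(POM ≤ 2% given benign)
- q = share of benign reads at exactly 2%; m = share of malignant reads at exactly 2%

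**Formulas**
- As written (W): NLR = (1 − se)/(sp − q); PLR = se/(1 − sp + q)
- Rule A, 2% negative: NLR = (1 − se)/sp; PLR = se/(1 − sp)
- Rule B, 2% positive: NLR = (1 − se − m)/(sp − q); PLR = (se + m)/(1 − sp + q)

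**Direction**
- W relative to A: NLR is multiplied by sp/(sp − q) ≥ 1 and PLR by (1 − sp)/(1 − sp + q) ≤ 1. Only benign ties matter.
- W relative to B: NLR is multiplied by (1 − se)/(1 − se − m) ≥ 1 and PLR by se/(se + m) ≤ 1. Only malignant ties matter.

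**Size within one modality.** The documents give neither tie shares nor expected sensitivity and specificity at 2%, so all of these are assumed: se = 0.97, sp = 0.40. Cells show NLR / PLR.

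| q, m | As written | Rule A | Rule B |
|---|---|---|---|
| 0, 0 | 0.075 / 1.617 | 0.075 / 1.617 | 0.075 / 1.617 |
| 1%, 0.1% | 0.077 / 1.590 | 0.075 / 1.617 | 0.074 / 1.592 |
| 2%, 0.2% | 0.079 / 1.564 | 0.075 / 1.617 | 0.074 / 1.568 |
| 5%, 0.5% | 0.086 / 1.492 | 0.075 / 1.617 | 0.071 / 1.500 |

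Last row, as written: 0.03/0.35 = 0.086 and 0.97/0.65 = 1.492.

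For scale, with 15 readers there are 4 × 75 × 15 = 4,500 benign reads per modality at 480 masses and 7 × 75 × 15 = 7,875 at 840. One percentage point of q is thus 45 or about 79 reads. Malignant reads number 4 × 45 × 15 = 2,700 and 7 × 45 × 15 = 4,725.

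**Imagio relative to IUS**, with the same se and sp in both reads. These tie shares are deliberately larger: m = 1.0% places one third of the malignant reads at or below 2% (0.010/0.030) on exactly 2%.

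1. Benign ties 6% IUS and 2% Imagio, equal malignant ties. As written and under B, relative NLR is 0.34/0.38 = 0.89 and relative PLR is 0.66/0.62 = 1.06. Under A both are 1.00.
2. Benign ties 2% in both, malignant ties 1.0% IUS and 0.5% Imagio. As written and under A both ratios are 1.00. Under B relative NLR is 0.025/0.020 = 1.25 and relative PLR is 0.975/0.980 = 0.99.
3. Benign ties 3% and 1%, malignant ties 1.0% and 0.5%. As written, relative NLR is 0.37/0.39 = 0.95 and relative PLR is 0.63/0.61 = 1.03. Under A both are 1.00. Under B they are (0.025/0.39)/(0.020/0.37) = 1.19 and (0.975/0.61)/(0.980/0.63) = 1.03.

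Cases 1 and 2 each agree with one coherent rule, so they show sensitivity to the choice of tie rule. In case 3 the written rule matches neither A nor B; the discrepancy is mainly in NLR.

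**The case against.** The strongest reply is that SAP 2.1.11 already settles the matter. It describes BI-RADS 3 as including 2% and then refers to this cutoff, so 2% would be a negative read and Table 1 is a one-symbol slip. That is a reasonable reading and supports the example fix below. It does not remove the problem: Table 1 is where the definitions are stated, it says otherwise, and Protocol 10.9 uses the cutoff sentence without the inclusive range.

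Second, no text expressly ties NLR and PLR to Table 1's inequalities, and the cited method for paired binary tests presumes one result per read. That is fair, and the link is an inference. But the NLR/PLR row directly follows those definitions, uses observed sensitivity and specificity, and offers no alternative cutoff.

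Third, the effect may be trivial. The expanded BI-RADS 3 scale may reduce ties, and at q = 1%, m = 0.1% NLR moves only from 0.075 or 0.074 to 0.077. The written rule never flatters a single modality. The 1% and 3% repeats bracket sensitivity and specificity, because a 2% read is positive at 1% and negative at 3% under either inequality, and rough bounds on the NLR and PLR point estimates follow. The planned POM summaries might also reveal a pile-up. All of this stands and limits the importance of the point, but none of it supplies a coherent rule for the NLR and PLR tests.

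**Conclusion.** The concern holds: the definitions are wrong as written. The logical inconsistency is certain. Its numerical effect is unknown, because the documents give no tie frequency, and it is zero if no read equals 2%. Within a modality, NLR is never lower and PLR never higher than under either coherent rule. The Imagio versus IUS comparison departs from Rule A only if benign ties affect the two reads unequally, from Rule B only if malignant ties do, and from both only if both do. All sizes shown rest on assumed sensitivity, specificity and tie shares. The extension to NLR and PLR assumes they use Table 1's definitions. The point should be fixed because it touches two label-bearing tests and the correction is very cheap.

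**What to change.** Before database lock, reconcile SAP 2.1.9 (Table 1) with SAP 2.1.11 in one complementary analysis rule. For example, POM of at most 2% is negative and POM above 2% is positive, which fits the inclusive range in SAP 2.1.11. State that sensitivity, specificity, NLR and PLR all use this rule, and apply the same inequality convention at the 1%, 3%, 4%, 5%, 6% and 7% cutoffs. Report the number of reads at exactly 2% by modality and truth status. This concerns the analysis rule only and sets no clinical threshold.

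The cost is a one-symbol correction, one sentence on NLR, PLR and the other cutoffs, one count table and a programming check. No new data are needed, and the primary analysis and sample size do not change.

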2.1.10. Hypotheses to be Tested

The test of the primary hypothesis is powered to detect a 10% absolute specificity advantage (superiority) as the alternative hypothesis with no specificity advantage as the null hypothesis. The primary endpoint will be evaluated in the following testable hypotheses:

$$H_0: S_{\text{Imagio}} = S_{\text{IUS}}$$

$$H_1: S_{\text{Imagio}} \neq S_{\text{IUS}} \text{ representing a 10\% absolute increase}$$

where S_{Imagio} and S_{IUS} represent specificity, values associated with Imagio (IUS + OA) and IUS.

The following hypothesis tests will be applied using the observed estimates for the following secondary endpoints:

- NLR:
 - $H_0: \text{NLR}_{\text{IUS}} = \text{NLR}_{\text{Imagio}}$ vs
 - $H_A: \text{NLR}_{\text{IUS}} \neq \text{NLR}_{\text{Imagio}}$ representing a reduction
- PLR:
 - $H_0: \text{PLR}_{\text{IUS}} = \text{PLR}_{\text{Imagio}}$ vs
 - $H_A: \text{PLR}_{\text{IUS}} \neq \text{PLR}_{\text{Imagio}}$ representing an increase
- Partial ROC AUC:
 - $H_0: \text{pAUC}_{\text{IUS}} = \text{pAUC}_{\text{Imagio}}$ vs
 - $H_A: \text{pAUC}_{\text{IUS}} \neq \text{pAUC}_{\text{Imagio}}$ representing an increase

Hierarchical testing will be applied to seek labeling claims if warranted by the pre-defined testing procedure (see Section 2.1.11.4).

2.1.11. Data Analysis Methodology

Data Analyses

As for the PIONEER Pivotal Study, analyses will be based on independent readers for POM, BI-RADS and feature scores (IUS, Imagio (IUS+OA)) individually and overall. There is a formal hypothesis test for the primary endpoint and the three secondary endpoints. Hierarchical testing will be in place to control the Type I error. Truth (determination of malignant biopsy, benign biopsy, HR or TPB) will be taken from the PIONEER Pivotal Study. All CB masses (n=29) will be excluded from all analyses; these masses will be replaced in order to preserve final analysis power.

The specificity advantage of Imagio (IUS+OA) vs. IUS will be compared at fixed 98% sensitivity. The software package OR-DBM MRMC [Version 2.5 or later] will be used for this analysis of OA gain as interpolated from the ROC curves.

Specificity and sensitivity will be calculated by reader and overall for IUS, Imagio (IUS+OA), and the pairwise difference [PROC GENMOD, see Table 1]. Specificity and sensitivity will be calculated using the 2% POM cutoff for IUS and for IUS+OA; and then for 1%, 3%, 4%, 5%, 6%, and 7% cutoffs to assess robustness. In clinical practice, the POM Scores (0-100) are standardized such that a BI-RADS 3 (probably benign) shows a likelihood of cancer to be > 0% up to 2% inclusive.

Specificity and sensitivity are calculated using this fixed 2% cutoff. Please be assured that the OR-DBM MRMC 2.51 (Hillis) software does not pick or use a fixed cutoff. [REDACTED]

[REDACTED] The gain in specificity can be computed at a wide range of sensitivities. The 98% sensitivity corresponds to a 2% false negative (FN) rate, but this unrelated to the use of a fixed 2% POM cutoff for clinical decision making.

NLR and PLR will be analyzed using the logarithmic transformation and the delta method. Calculations will be performed using MATLAB script: [REDACTED] [REDACTED]

Last, pAUC for fixed 95% to 100% sensitivity will also be analyzed using OR-BDM MRMC.

The sample size for the READER-02 pivotal study was calculated using method implemented in the MRMC Sample Size Program 1.0 for Diagnostic Studies, by Hillis, Obuchowski, and Birnbaum. These sample size results may be confirmed by other packages such as nQuery, PASS, and SAS [PROC POWER].

POM summary statistics for IUS, Imagio (IUS+OA), and the pairwise difference will be displayed by diagnostic category and compared using a Wilcoxon Rank Sum test. POM scores for benign masses will be displayed for masses with and without mammograms.

OA feature scores including internal total, external total, and overall total scores will be summarized to describe the distribution of individual feature scores by diagnosis, with a Wilcoxon statistical test for the difference in the distributions between malignant and benign. Feature scores for benign masses will be displayed for masses with and without mammograms.

2.1.11.1. Adjustments for Covariates

No adjustments for covariates are planned.

The primary and secondary endpoints will be rerun for the subgroups with and without mammograms.

2.1.11.2. Handling of Dropouts or Missing Data

Missing reader data will be reported (see protocol deviations). No imputation is planned for any excluded study data. The analysis methods can accommodate missing reader data.

2.1.11.3. Interim Analyses and Data Monitoring

Plan

The interim analysis (IA) is to re-estimate sample size to avoid running an underpowered study. The IA will be performed by an unblinded statistician familiar with the study data. The Sponsor and all other parties will remain blinded to the results. The only communication to the Sponsor will be the final sample size recommendation. The sample size may be increased up to 840 masses from the initial 480 masses in order to achieve 80% power for the primary endpoint. This recommendation will be based solely on variance parameters re-estimated in the IA (but not the effect size). Thus, these IA results fall into the category of non-comparative results. Thus, the IA has negligible effect on the Type 1 error. The IA will be based on the total variance estimate (inclusive of both reader and imaging modality variations) so the IA remains 'non-comparative' since the interim treatment effect was not used to compute the final sample size.

Methodology

The sole IA goal is to compute the final sample size based on the primary endpoint. The sample size re-estimation (SSRE) will be performed without any adaptation. SSRE will be conducted to detect the 10% absolute advantage in specificity for fixed 98% sensitivity, given that this is an established criterion agreed upon with FDA. The standard deviation (from reader as a random effect) is not known. There will be no preplanned or performed

assessments for futility, stopping for early efficacy, dropping readers, altering the 10% effect hypothesis, or any other adaptation. Therefore, this is classic SSRE.

Huang and Chen (1) reference this application as distinct from his discussion of adaptive designs. Our IA is based entirely on non-comparative data, that is, no information about treatment effects were incorporated into the decision process. For this SSRE situation (a non-comparative interim), it can be shown that performing analyses at the conventional one-sided 0.025 significance level has a negligible effect on the Type 1 error probability (FDA Guidance on Adaptive Trials (2), Wittes (3), Kieser and Friede (4), Friede and Kieser (5), among others). Wittes advises that the alpha spend is small when the observed variance is less than the assumed variance (as per the interim analysis) without accounting for imaging modality. Huang and Chen advise that the alpha spend is small when the conditional power exceeds 60% which is the case when a 10% delta is assumed; any delta effect would further reduce the reader variance. They specifically state that “for conditional power within a range of 0.37 and 0.80, the sample size can be increased while leaving the critical test value unchanged”; this is the fundamental premise of the promising zone. Thus, the alpha spend for conducting the planned interim analysis is small.

From a testing perspective, the conclusions should hold in recognition that the p-value is a Z-score whether derived from a one-sample or a two-sample test independent of the model used (Huang or Hillis). All alpha adjustment depends on a linear combination of Z-scores (6) for respective Z-scores prior to and after the pre-planned interim analysis. Thus, first principles all lead to the conclusion that the alpha spend is small enough to ignore. Our estimate is that the alpha spend is no more than 0.01% under the given conditions. The minimal alpha spend derives from the abundant two-sample literature to apply to our paired sample setting with no published literature.

Timing

A blinded interim analysis is planned for this study after all readers complete the reads for the first three blocks (360 - 10 CB masses = 350 complete image sets). The CB masses (n=10) will be excluded from the interim analyses.

The interim analysis will solely re-estimate sample size based on the primary endpoint; it will not be used to modify the alternative hypothesis. Neither futility nor efficacy will be assessed. The following recommendations will be issued to Seno by the unblinded statistician at the interim timepoint:

1. Sample Size Calculation:

- One additional block (480 masses) is required OR
- Two additional blocks (600 masses) are required OR
- Three additional blocks (720 masses) are required OR
- Four additional blocks (840 masses) are required OR
- Four additional blocks (840 masses) are not sufficient but reads should continue because there is a reasonable chance to reach statistical significance based on the conditional power assuming the alternative hypothesis holds.
- Four additional blocks (840 masses) are not sufficient, reads should not continue because there is not a reasonable chance to reach statistical significance

based on the conditional power assuming the alternative hypothesis holds

Execution

The unblinded biostatistician will only evaluate the overall standard deviation which was the nuisance parameter driving sample size for the fixed 10% difference to be detected. The unblinded biostatistician will not need to take the observed delta into account. Other than the preplanned sample size calculation to determine the remaining blocks required to complete the study, no other information will be revealed to the Sponsor or to any other members of the analysis team. The IA will be executed to the blinded principle.

